SA 1 (primary): Eradication rate at one year will be compared between current recruits (i.e. study patients on adjuvant liquid alginate) and historical controls. Patients will be matched by type of therapy, and to the best of our ability, length of Barrett's.

SA2 (secondary): To compare the duration of treatment required to achieve complete endoscopic eradication of BE in patients treated with the combination of PPI and liquid alginate solution vs. those treated with PPI alone.

SA 3 (tertiary): To compare the number of treatment sessions required to achieve endoscopic eradication of BE in patients treated with the combination of PPI and liquid alginate solution vs. those treated with PPI alone.

Study Design

This is a pilot prospective cohort study at a single tertiary care center. Patients with BE and proven dysplasia (high or low grade) or risk of other abnormality presenting to our tertiary care center interested in endoscopic treatment will be asked to participate in the study. Participation will involve taking 10 mL of Gaviscon Advance four times daily along with twice daily PPI during the treatment duration. The control group will be a historical cohort of Barrett's esophagus patients treated in the last 5 years by the same endoscopists using similar approaches—these are patients who were prescribed twice daily PPI therapy alone during treatment.

Eligibility Criteria

Patients who are already scheduled for treatment of their dysplastic Barrett's esophagus or risk of other abnormality who are planning to undergo EMR, or ablation therapy with cryotherapy (spray or balloon) and/or RFA (with or without EMR) will be eligible for enrollment.

Inclusion criteria (all must be present):

- (1) Age ≥ 18
- (2) Patients already previously scheduled for treatment of complicated Barrett's esophagus
- (3) Long Segment Barrett's ($>3\text{cm}$)

Exclusion criteria:

- (1) Moderate to severe renal impairment, as defined by eGFR < 60 for 2 consecutive readings
- (2) Lack of capacity for decision-making
- (3) Allergy to hydroxybenzoates

- (4) Patients with uncontrolled hypertension or decompensated heart failure
- (5) Pregnancy- patients of child-bearing potential will be tested.
- (6) Patients with elevated calcium or potassium on screening laboratory testing (labs completed within the last month)

Enrollment

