All enrolled subjects will be followed until resolution of Barrett's is achieved, as confirmed by biopsy and endoscopic visualization. A measurement system referred to as the Prague classification³² will be used to document areas of the esophagus with Barrett's and to assess improvement from one endoscopy to another. This system allows the endoscopist to record the area of Barrett's involved by describing the area involved that is circumferential in nature and the area that is patchy. Decrease in surface area involved will help guide the aim for the study. During treatment sessions, pertinent clinical and endoscopic data will be collected (see Appendix A). Immediately prior to each treatment visit, an office visit will take place at the MUSC Gastroenterology endoscopy/outpatient clinic with study personnel including the PI, research coordinator, and/or fellow/resident participating in the study, which will serve to collect data regarding blood pressure, surveillance serum chemistries, treatment experience, adverse events to the drug, or any other issues (see Appendix B). Adherence to the medication regimen will be done by asking patients to bring in all used and unused bottles. IDS will assist in calculating how much drug has been taken and this data will be recorded at each visit. These data will then be entered into a coded RedCap database. At approximately six week intervals, the study research coordinator will call to verify medication regimen adherence as well as any adverse events associated with the study drug.

From the time of biopsy proven remission, patient medical records will be reviewed for up to 2 years to evaluate recurrences rates.

Outcomes

Eradication rate of intestinal metaplasia (complete remission of intestinal metaplasia – CRIM) at one year will be the primary outcome. The length of time to eradication and the number of endoscopic procedures required for CRIM will be the secondary and tertiary outcomes. CRIM will be defined as visual endoscopic evidence of neo-squamous epithelium occupying previous area of Barrett's epithelium combined with biopsies showing normal squamous esophageal epithelium without intestinal metaplasia.

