This is a single center study which will be conducted solely at MUSC. Patients will be monitored with a telephone call every six weeks as mentioned above and they will be provided with information to get in touch with the study team if they have problems between their visits.. Enrollment will be ongoing until an adequate number of subjects have been recruited. Thus, we anticipate that the study can be completed within 2 years.

Monitoring

All study data will be monitored routinely for completeness, timeliness, and consistency by the project manager. Data accuracy will be verified on a quarterly basis by the project manager and principal investigator. Due to a relatively small “n”, all subjects’ data will be reviewed. Discovered discrepancies between recorded study data and information found in medical records will be addressed through discussions between the PI and research coordinator. Subjects may be withdrawn from the study if they are lost to follow up, or if they endorse lack of compliance with liquid alginate solution and/or PPI therapy.

Safety

Gaviscon Advance is considered a very safe medication with a very mild side effect profile. It is widely available in the UK but not available in the US. An FDA IND application has been filed for its use for this study. Gaviscon Advance will be purchased directly from the pharmaceutical company, Reckitt Benckiser. Each 10 mL oral suspension contains 1g sodium alginate and 200 mg potassium hydrogen carbonate (active ingredients). The formulation also contains calcium carbonate, carbomer, sodium saccharin, sodium hydroxide, and so any patients who have been advised to restrict their diet from any of these substances should consult a doctor before taking Gaviscon Advance. Patients who suffer for have suffered from significant kidney or heart disease should speak with a physician before taking Gaviscon. Finally, the formulation includes methyl and propyl para-hydroxybenzoates which may cause allergic reactions (less than 1 in 10,000 patients), including skin rash, itching, difficulty breathing, dizziness, or swelling. Overdosing of the medication may cause bloating. Please see summary of product characteristics – Appendix D).

Any adverse event, either related to Gaviscon Advance or not, will be recorded in pre-treatment clinic and/or treatment visits, and will be evaluated by a safety review committee (see below).

Safety Review Committee

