A safety review committee will be assembled for this clinical study. This committee will be composed of 3 persons who are not study investigators. The overall goals of the committee will include the following: 1) identify unacceptably slow rates of accrual, 2) identify high rates of ineligibility, 3) identify protocol violations that suggest clarification of changes to protocol are needed, 4) identify unexpectedly high dropout rates that threaten the trial’s ability to produce credible results, 5) ensure the credibility of the study, 6) ensure the validity of study results, and most importantly, 7) protect the safety of trial participants. The safety review committee will meet quarterly. If irregularities are identified in any of the goal areas listed above, the committee will propose changes to the protocol or study infrastructure in order to remedy the problem. In the event of a severe problem, the committee may advise termination of the study.

Potential Problems and Pitfalls

There are several potential pitfalls that may affect this study. However, if these are anticipated and managed appropriately, we believe they will not significantly impact the validity of the findings.

We have been conservative with the estimate of the anticipated number of subjects during the funding period. There are typically only several patients at MUSC's GI clinic per month that present with dysplastic Barrett's (or Barrett's with IMC) who are naïve to treatment. Therefore, we are proposing a pilot study with a conservative initial enrollment goal of 20 patients. This number can be increased to compensate for subjects who are potentially withdrawn or LTFU. If this pilot study proves to be informative, a multicenter initiative would be the next step.

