Another challenge will be ensuring subject compliance with both PPI and liquid alginate therapy. This is particularly salient in patients who experience improvement in symptoms, and feel that they don't need to take medicine anymore, especially since the recommended dose of the study drug will be four times a day. We will contact the patients in between each 2-3 month visit, via telephone call and routinely reiterate the importance of medication compliance. We will also accurately record adherence, as mentioned above, by asking patients to bring in all bottles (used and unused) that were dispensed to them. Moreover, in the cases that prompted this line of research, we observed benefit associated with only twice daily dosing of alginate, making it feasible that our hypotheses could be met even if half the recommended dose is taken.

Lastly, the small sample size will limit the validity and generalizability of our observations. The numbers may be further be limited as patients undergoing RFA and cryotherapy will be analyzed separately. As mentioned above, this is intended to be a hypothesis-generating study that may inform the design of a larger multi-center initiative.

References

2. Boni, L., A. Benevento, S. M. Shimi, and A. Cuschieri. "Free Radical Production in the Esophago-gastro-duodenal Mucosa in Response to Acid and Bile." *Diseases of the Esophagus Dis Esophagus* 19.2 (2006): 99-104. Web.
3. Castell, Donald O., Christine Boag Dalton, David Becker, Jane Sinclair, and June A. Castell. "Alginic Acid Decreases Postprandial Upright Gastroesophageal Reflux." *Digest Dis Sci Digestive Diseases and Sciences* 37.4 (1992): 589-93. Web.
4. Chiu, C.-T., C.-M. Hsu, C.-C. Wang, J.-J. Chang, C.-M. Sung, C.-J. Lin, L.-W. Chen, M.-Y. Su, and T.-H. Chen. "Randomised Clinical Trial: Sodium Alginate Oral Suspension Is Non-inferior to Omeprazole in the Treatment of Patients with Non-erosive Gastroesophageal Disease." *Alimentary Pharmacology & Therapeutics Aliment Pharmacol Ther* 38.9 (2013): 1054-064. Web.

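### Admitted non-compliance can end outcome follow-up in the alginate cohort only, which can bias one-year CRIM and median time to CR in an unknown direction

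*Combined protocol and SAP*

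**What the plan says.** All references are to the combined protocol and SAP.

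- **Monitoring.** Withdrawal from the study is permitted, at discretion, for loss to follow-up or for patients in the prospective cohort "if they endorse lack of compliance with liquid alginate solution and/or PPI therapy". The wording concerns leaving the study, not stopping alginate.
- **Study Design.** Of the historical controls it says: "these are patients who were prescribed twice daily PPI therapy alone during treatment". Under Hypotheses & Specific Aims, matching is on type of therapy and, where possible, Barrett's length. Adherence and retention are not mentioned.
- **Follow-up Assessments.** "All enrolled subjects will be followed until resolution" of Barrett's, with no reference to withdrawn patients. Adherence is measured from returned bottles. Record review has a stated starting point: "From the time of biopsy proven remission, patient medical records will be reviewed".
- **Outcomes.** CRIM "at one year will be the primary outcome"; time to eradication and number of procedures follow.
- **Sample Size Calculation and Statistical Consideration.** Kaplan-Meier curves, an exponential rate for each cohort, and a rate difference with a 95% CI. The one censoring rule covers patients without CR at study end.
- **Potential Problems and Pitfalls.** On the target of 20 patients: "This number can be increased to compensate for subjects who are potentially withdrawn or LTFU".
- **Safety Review Committee.** One of its goals is to "identify unexpectedly high dropout rates".

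**The concern.** The withdrawal trigger is something a patient does after enrollment, and it can operate in one cohort only. A control who skipped PPI doses stays in the historical data. An alginate patient who admits to the same can be taken out of the study before the outcome is known. The two cohorts could then differ in one-year CRIM and time to CR with no alginate effect.

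The sign cannot be predicted. Non-compliers may clear more slowly if poor PPI intake impairs healing. They may clear faster if feeling better is what leads them to stop; Potential Problems and Pitfalls says of the compliance problem: "This is particularly salient in patients who experience improvement in symptoms". If withdrawal is related to prognosis, censoring at withdrawal does not remove the bias, because the patients still at risk no longer represent those who left.

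At stake is the credibility of the estimates meant to inform a later randomized trial. No hypothesis test is planned, so type I error is not the issue.

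**Working it through.** The plan gives no power calculation and no expected withdrawal rate, so there is no stated figure to reproduce. The calculation below shows only how far the estimates could move.

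**From the plan:** exponential time to CR; median about 22 months under current treatment; about 20 patients; one-year CRIM as primary outcome.

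**Assumed:** no drug effect; 24 months' follow-up per patient (the plan gives 2 years only as anticipated study duration); non-complier share q of 0.2 or 0.3; non-compliers clear at h times the adherent rate, with h from 0.5 to 1.5; withdrawal times uniform over 0–24 or 0–6 months.

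**Step 1, baseline.** Rate = ln 2 / 22 = 0.0315 per month. One-year CRIM = 1 − exp(−12 × 0.0315) = 31.5%. The plan's example of improvement, 18 months, corresponds to 37.0%.

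**Step 2, withdrawal unrelated to prognosis, censored at withdrawal.** Events and person-time shrink in proportion, so the estimated median stays at 22.0 months. There is no bias in the median.

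**Step 3, withdrawal related to prognosis, censored at withdrawal.** Solve (1 − q)exp(−12L) + q·exp(−12hL) = 0.685 for the adherent rate L, so that the whole cohort still has 31.5% CRIM at one year.

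Per patient at rate r followed to 24 months, expected events are 1 − exp(−24r). With withdrawal uniform on 0 to a, they are 1 − (1 − exp(−ra))/(ra). Person-time is expected events / r. The estimated median is ln 2 × total person-time / total events.

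Example, q = 0.3 and h = 0.5, so L = 0.0376 and hL = 0.0188:

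- Adherent: 0.5945 events and 15.81 months per patient.
- Non-compliers, withdrawn in months 0–6: 0.0543 events and 2.89 months. Median = 0.693 × (0.7 × 15.81 + 0.3 × 2.89) / (0.7 × 0.5945 + 0.3 × 0.0543) = 0.693 × 11.93 / 0.4324 = 19.1 months.
- Non-compliers, followed to 24 months: 0.3632 events and 19.32 months. Median = 0.693 × 16.86 / 0.5251 = 22.3 months.

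| q, h | Censored, withdrawal 0–24 mo | Censored, withdrawal 0–6 mo | Followed to 24 mo |
|---|---|---|---|
| 0.2, 0.67 | 21.4 | 20.8 | 22.1 |
| 0.3, 0.5 | 20.7 | 19.1 | 22.3 |
| 0.2, 1.25 | 22.4 | 22.8 | 22.0 |
| 0.3, 1.5 | 23.1 | 24.3 | 22.1 |

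Entries are estimated medians in months. The matching Kaplan-Meier one-year CRIM is 30.8–32.4% for withdrawal over 0–24 months and 29.2–35.1% over 0–6 months, against a true 31.5%. With 18 or 36 months' follow-up in place of 24, the first column spans 21.0–22.8 or 20.3–23.4.

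**Step 4, sampling error.** In 200,000 simulated cohorts of 20 with no withdrawal, 95% of estimated medians fall between about 12.5 and 45 months.

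**The case against.** **The plan may already keep everyone.** Withdrawal is discretionary, Follow-up Assessments covers all enrolled subjects, and the statistical section speaks of about 20 enrolled patients. Kaplan-Meier and exponential likelihood methods ordinarily censor early leavers, and Step 2 shows no bias in the median if leaving is unrelated to prognosis. This stands as a limit on the claim. It does not remove the Monitoring rule, which conflicts with following everyone whenever it is used.

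**A reader might infer that withdrawn patients are deleted and replaced.** On that reading the shift is larger. If 21% were withdrawn before CR for reasons unrelated to prognosis and deleted, the median would be 18.7 months. If 3 of 20 would-be non-responders were excluded, it would be 17.3, past the 18-month example with no drug effect. The documents do not support this reading. The enrollment sentence raises numbers and drops no one from analysis, and nothing suggests that withdrawn patients would all be non-responders. Nor do the documents support inferring that alginate must look better, or that the controls are unmatched. What is missing is a counterpart withdrawal rule.

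**The effect is small beside sampling error in a descriptive, hypothesis-generating pilot.** True, and none of the censored scenarios crosses 18 months. But a bias adds to sampling error and is invisible in the CI.

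**Safeguards exist.** Six-weekly calls, bottle counts and the safety committee may reduce or reveal non-adherence and dropout. None supplies an analysis rule. Records may exist in routine care at the same center, and Monitoring already compares study data with medical records, so the data gap may be modest.

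**An on-treatment estimate is legitimate in a pilot.** Yes, if labelled as such and not substituted for the primary analysis.

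**Conclusion.** The concern holds as a one-sided withdrawal rule that can end outcome follow-up on post-enrollment behaviour and is not reconciled with two other sections. It is a risk of bias of unknown sign. In the illustration the median moves from 22 to about 20.7–23 months, or 19.1–24.3 with early withdrawal, against 22.0–22.3 with continued follow-up. Every withdrawal share, rate ratio and timing behind those figures is assumed, and sampling error with 20 patients is larger.

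The plan also gives its own reason to keep partly adherent patients: Potential Problems and Pitfalls argues that the hypotheses could hold with half the recommended amount taken. The change should be made, but the point does not undermine the pilot as a whole. Confidence is medium.

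**What to change.** 1. In Monitoring, remove non-compliance as a reason for withdrawal from outcome follow-up and analysis. Whether a patient continues alginate is a separate matter, not addressed here.
2. Keep every patient who starts alginate in the primary one-year CRIM and time-to-CR analyses. Continue to collect endoscopy and biopsy results after alginate stops. Extra enrollment adds patients and replaces no one in the analysis.
3. Censor only patients who are truly lost or withdraw consent, at their last outcome endoscopy. Report one-year CRIM with a sensitivity analysis that counts unknown status as not eradicated. Handle loss to follow-up the same way in the controls, as far as existing records allow.
4. Use bottle-return adherence only in a labelled on-treatment sensitivity analysis.
5. Reconcile Follow-up Assessments, Monitoring and Potential Problems and Pitfalls.

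**Cost.** About a paragraph of wording, plus routine-care outcome records for patients who stop alginate; adherence is already recorded. Non-adherence may dilute the estimated effect, and censoring of truly lost patients may still be informative.
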